### 3.5 Sensitivity analyses of primary outcome

1. **Assessing our primary outcome using multivariable log-binomial models that adjust for unbalanced characteristics or pre-specified characteristics measured in the baseline survey (e.g., ART status).** We will compare categorical variables using Chi-square tests and determine between which arms the variable in question is unbalanced using pairwise comparisons. We will compare balance of continuous variables using ANOVA. If multivariable log-binomial models fail to converge, we will use a modified Poisson regression with robust estimates of variance. Comparison will be made to logistic regression models as well if the proportion of the outcome (those who accept and complete treatment) in our population is rare ( $\leq 15\%$ ). Log binomial regression will be used for secondary (multivariable adjusted) analyses. If multivariable log-binomial models fail to converge, we will use a modified Poisson regression with robust estimates of variance. Participants who decline to initiate 3HP after randomization will be counted as not accepting/completing treatment in the primary (ITT) analysis and will be followed over time for clinical outcomes.

Analyses will be done in Stata using *glm, family(binomial) link(log)* command for log binomial models, or *glm, family(poisson) link(log) vce(robust)* command for modified Poisson models. The log binomial regression model will take the general form of:

$$\log(p) = \beta_0 + \beta_1 X + e, \dots \quad \text{Equation 1}$$

2. **Assessing our primary outcome to estimate a per protocol estimate that reflects the difference in treatment completion rates in patients that actually initiate treatment.** Thus, participants who were randomized but declined to initiate treatment will be excluded from this analysis. Note: the per protocol analysis of the primary outcome will be equivalent to our assessment of the secondary outcome specified in the trial protocol of treatment completion (the proportion of those who complete at least 11 of 12 doses within 16 weeks of treatment initiation among those who take at least one dose of 3HP). Assessment of the per protocol outcome will involve 1) unadjusted comparisons of risk ratios and 97.5% two-sided CIs of effectiveness between arms, 2) simple calculation (using the exact binomial CIs) of the

effectiveness of each delivery option, with a target of >80%, and 3) comparisons of risk ratios and 97.5% two-sided CIs of effectiveness between arms, adjusted for unbalanced characteristics or pre-specified characteristics measured in the baseline survey. We will assess for differences in the ITT and PP analysis populations by comparing baseline characteristics such as age, sex, antiretroviral therapy (**ART**) status, time on ART and prior TB.

3. **Assessing our primary outcome to estimate an as treated estimate that reflects the difference in treatment completion rates in patients** classifying participants based on which delivery strategy they actually received, irrespective of which arm they were allocated to. This will involve 1) allocating choice participants to either DOT or SAT arm, 2) making unadjusted comparisons of risk ratios and 97.5% two-sided CIs of effectiveness between arms, 3) simple calculation (using the exact binomial CIs) of the effectiveness of each delivery option, with a target of 80% and 4) comparisons of risk ratios and 97.5% two-sided CIs of effectiveness between arms, adjusted for unbalanced characteristics or pre-specified characteristics measured in the baseline survey.

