### 3.3 Baseline assessment of patient characteristics

Baseline demographic and clinical characteristics will be assessed for all patients across arms in order to assess achievement of balance across arms by randomization. Characteristics may include but are not limited to: age, sex, prior TB, multidimensional poverty index (**MPI**), ART status, and years on ART.

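### The adjusted sensitivity analyses have no closed covariate list, and their imbalance route picks covariates by baseline significance tests that usually miss prognostic variables; the unadjusted primary analysis is unaffected

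*SAP*

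**What the plan says.** SAP 3.5 is headed "Sensitivity analyses of primary outcome". Its item 1 fits multivariable log-binomial models that "adjust for unbalanced characteristics or pre-specified characteristics measured in the baseline survey", with ART status the only example given. Imbalance in categorical variables is judged by chi-square tests, which then "determine between which arms the variable in question is unbalanced using pairwise comparisons". For continuous variables: "We will compare balance of continuous variables using ANOVA". No p-value or other cut-off is stated, and association with completion is not a criterion.

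The per-protocol and as-treated analyses (items 2 and 3) each include risk ratios "adjusted for unbalanced characteristics or pre-specified characteristics measured in the baseline survey".

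The nearest thing to a candidate list is SAP 3.3, and it is open: "Characteristics may include but are not limited to: age, sex, prior TB", followed by the poverty index, ART status and years on ART. SAP 3.6 lists subgroup variables, among them reimbursement level, but does not tie them to adjustment.

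The primary analysis in SAP 3.4 is the unadjusted intention-to-treat risk ratio with a 97.5% interval and Fisher's exact test at 0.025. The protocol's list of secondary analyses adjusts for baseline-survey characteristics and mentions no balance test. SAP 2.3 gives the SAP precedence.

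**The concern.** Between arms formed by randomization, a baseline significance test examines a null hypothesis known to be true. A small p-value there reflects luck and says nothing about whether the variable predicts completion. Used to select covariates, such tests let in variables of no prognostic value and usually leave out useful ones.

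The unresolved "or" makes this worse. With no threshold and no closed list, two analysts following the SAP faithfully could fit different adjusted models, and each could decide after seeing the data. These models are the planned robustness check on the primary result, and a check whose covariates are chosen late reassures less than one fixed beforehand. At stake are some precision and the credibility of the sensitivity analyses.

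**Working it through.** **1. The plan's own figure.** The documents give no power figure for the adjusted analyses; theirs is for the unadjusted comparison. Inputs: 552 per arm, two-sided alpha 0.025, 70% against 80%, and the protocol's 10% loss, so 552 × 0.90 ≈ 497 per arm. Power is 0.909 with continuity correction and 0.911 by Fisher's exact test, against 0.90 stated. The SAP's 5% loss (524 per arm) gives 0.925 to 0.926. The two loss figures need reconciling, but that is a separate matter. The covariate rule does not enter this calculation.

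**2. Flags by luck.** Assumptions: a 5% threshold (the SAP gives none) and independent covariates. For the six variables named in SAP 3.3, 1 − 0.95^6 = 0.265; for five, 1 − 0.95^5 = 0.226. Years on ART and ART status are plainly related, so 26% is a guide rather than an exact figure.

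**3. Does the imbalance route find prognostic covariates?** A simulation of three arms of 552 (1,500 runs per setting, no treatment effect, 70% completion, modified Poisson model, flags at p<0.05) flagged a given prognostic covariate in only 4 to 6% of trials, whatever its strength. At least one covariate was flagged in 24 to 27% of trials.

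The share of outcome variance explained by one binary covariate is R² = q(1−q)(p_a − p_b)² / [p(1−p)]. Take prevalence q = 0.30 and average completion p = 0.75. At odds ratio 3, p_a = 0.816 and p_b = 0.596, so R² = 0.21 × 0.0484 / 0.1875 = 0.054, and 552/(1 − 0.054) ≈ 584 per arm.

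| Assumed odds ratio | R² | Equivalent n per arm | Simulated variance cut, fixed adjustment | Simulated variance cut, test-selected |
|---|---|---|---|---|
| 1.5 | 0.7% | 556 | about 0% | about 0% |
| 2 | 2% | 564 | about 3% | about 1% |
| 3 | 5% | 584 | about 5% | about 2% |
| 5 | 12% | 624 | about 12% | about 3% |

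Test selection loses most of the gain available, but that gain is small unless the covariate is strong.

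**4. One strong covariate, assumed.** Take two arms of 552 with no loss. 40% of participants have 85% completion and the rest 65%, so 0.4 × 0.85 + 0.6 × 0.65 = 73% overall; alpha is 0.025. The estimates are standardised risk differences, and the rule adjusts only when the imbalance exceeds 1.96 SE.

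- One SE of imbalance is √(2 × 0.4 × 0.6 / 552) = 0.0295. About 26% of simulated trials have an imbalance of 1 to 1.96 SE, which the rule ignores.
- The mean imbalance in that band is (0.2420 − 0.0584)/(0.9750 − 0.8413) = 1.37 SE. The unadjusted estimate is then off by 0.20 × 1.37 × 0.0295 = 0.0081, or 0.8 percentage points in absolute value. The signed average is zero.
- Power for 73% against 83% is about 0.965 under the rule and 0.972 with fixed adjustment. With completion 3 points lower in each stratum (70% against 80%, the plan's first row) it is 0.948 and 0.957.
- Overall test size is 0.024 under the rule and 0.026 with fixed adjustment. Inside the band it is 0.028 and 0.026.

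**5. The non-randomized comparisons.** Item 2 of SAP 3.5 drops participants who decline after randomization. Item 3 moves choice-arm participants into DOT or SAT according to what they received. Differences between those groups can reflect selection, and a variable confounds if it is related both to group and to completion. A test of balance does not examine the second relation. The protocol promises methods such as inverse probability weighting for these estimands, with full details in the SAP; SAP 3.5 gives none. Adjustment by the rule quoted above is the only protection it states.

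**The case against.** The strongest reply is that the SAP does not rely on tests alone. It allows pre-specified characteristics as a second route, with ART status as an example, and the protocol's version has no tests. This is correct. A reader might infer that covariates are chosen solely by significance tests, or that p<0.05 is the planned cut-off; the SAP says neither. But the second route leads to no actual list, so what stands is that the choice remains open.

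The second reply is that nothing confirmatory is affected. This also stands. A reader might infer from the power and test-size figures that the trial's main conclusion or error rate is at risk. SAP 3.4 fixes an unadjusted primary analysis, and even the adjusted test shows no overall inflation in the illustration. The small excess appears only within one band of imbalance.

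Third, a 20-point prognostic effect is assumed and no document supports it. Step 4 also uses two-arm risk differences, whereas the SAP plans risk ratios and checks balance across three arms. This is fair. The three-arm modified Poisson results in step 3 point the same way and show how the gain shrinks for weaker covariates.

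Last, the argument that imbalance is only chance applies to the intention-to-treat sets. It cannot be carried over to the as-treated and per-protocol sets, where the objection to the rule is that it does not target confounders. The SAP does plan to compare baseline characteristics of the intention-to-treat and per-protocol populations, which is useful description but not a covariate rule.

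**Conclusion.** The point holds as a minor one. The SAP leaves the adjusted models for all three sensitivity analyses open to choice after the data are seen, and its imbalance route disregards prognostic strength. The primary estimate, test and power are unchanged.

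The cost of the rule is about one point of power and a 0.8-point absolute conditional error in roughly a quarter of trials, for one strong assumed covariate. At odds ratio 2 the variance forgone is about 2%. The 26% chance of a lucky flag depends on an assumed 5% threshold and six independent covariates. In the as-treated and per-protocol analyses the weakness is that confounding or selection is not addressed. Its size cannot be computed from the documents.

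**What to change.** In SAP 3.5, delete the chi-square, pairwise and ANOVA comparisons as a way of selecting covariates. Replace the "unbalanced or pre-specified" wording in items 1, 2 and 3 with one closed list chosen on prognostic grounds. Candidates already named in SAP 3.3 and 3.6 are age, sex, time on ART and prior TB; say explicitly whether the poverty index and reimbursement level at enrolment are in or out. State the coding of each variable, including where participants not on ART fall in time on ART. Use the same list in every adjusted model.

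In SAP 3.3, report baseline balance descriptively, without p-values. For the per-protocol and as-treated analyses, describe the list as confounder control and either supply the weighting details that the protocol promises or say that they are dropped.

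The covariate list and the balance reporting need SAP wording only: no new data, no change to sample size or to the primary analysis. It is a free improvement, best dated before outcome data by arm are examined.

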### 2.2 Primary hypotheses:

1. The proportion who accept and complete 3HP will be highest among PLHIV randomized to the informed choice arm.
2. The proportion of PLHIV who accept and complete 3HP can exceed 80% in a high HIV/TB burden setting.

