## 2.5 Sample Size

We estimated our sample size for the primary outcome (N=1656; 552/arm) based on a minimum clinically important difference of 10% in 3HP completion, comparing patient choice vs. DOT arms. Of note, the Centers for Disease Control and Prevention (**CDC**) TBTC iAdhere study of 3HP delivery strategies chose a 15% non-inferiority margin between DOT and SAT based on cost-effectiveness modeling in the US. We chose 10% to be more conservative because similar modeling studies have not been done in low-income settings, and because ours is not a non-inferiority design. To be maximally conservative, we applied a Bonferroni correction based on two independent comparisons (choice vs. DOT and choice vs. SAT). Assuming a two-sided alpha of 0.025, and 5% loss between consent and allocation, a sample size of 552 participants per arm (N=1656 total) is required to provide power of 0.90 to detect this difference (Table 3). This sample size will also give us power of 0.85 to detect a point estimate of at least 80% effectiveness in the patient choice arm, assuming a true effectiveness of 85%. If the true effectiveness rises to 86%, our power to show effectiveness >80% increases to 0.96. Power was calculated using the PS - Power and Sample Size program.

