### Power to detect 10% difference

Effectiveness		Power
DOT	Choice	
70%	80%	0.90
75%	85%	0.94
80%	90%	0.98
85%	95%	0.998

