## 3. Statistical Methods

### 3.1 General analysis principles

All primary analyses will involve assessment of all listed primary (effectiveness of delivery options and secondary (reach, effectiveness, adoption, and implementation) outcomes. Intent-to-treat (**ITT**) is a strategy for analyzing data that compares patients in the groups to which they were originally randomly assigned, irrespective of the treatment actually received. The ITT analysis will be the main statistical approach for determining intervention effectiveness. Per-protocol (**PP**) analyses reflect the inclusion in the analysis of patients who strictly adhered to the trial protocol. Based on these general analysis principles, the specific analyses to be conducted are described below.

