### 3.7 Analysis of secondary outcomes

Secondary outcome analysis will include:

1. **Reach outcome(s):** 1) Unadjusted comparisons across arms, and 2) simple calculation of the proportion of patients randomized who accept treatment in each arm.
2. **Effectiveness outcomes:** 1) Occurrence of AEs across arms will be assessed using Chi-square tests and logistic regression; 2) Incidence of active TB will be assessed using Kaplan-Meier curves, log-rank tests, and Cox proportional hazards methods as appropriate. Assessment for active TB occurs at 15-16 months post enrolment. Survival analyses will include:
  - o An assessment of the incidence rate of TB, comparing across arms (DOT vs. SAT vs. Choice) using Kaplan Meier, time-to-event analyses. We will estimate the difference in the Kaplan Meier and Cox proportional hazard estimators for the survivor functions, comparing the arms to get hazard ratios and 95% CIs.
  - o An assessment of the incidence rate per arm by drug compliance, which will include for each arm: a comparison of the incidence of active TB in those within the arm that complete at least 11 of the 12 doses within the allotted 16 weeks vs. the incidence of active TB in those within the arm that complete  $\leq$ 10 doses of 3HP. We will estimate the difference in the Kaplan Meier and Cox proportional hazard estimators for the survivor functions, comparing the arms to get hazard ratios and 95% CIs.

3. **Adoption outcomes:** For each process metric, we will report the monthly proportion (and 95% CI) number, or median (interquartile range (IQR)) to assess the implementation of intervention components in each arm.
4. **Implementation outcomes:** Quantitative data will be assessed using multivariable regression models to compare by study arm patient survey data including a) patient costs; b) scores on questions related to patient barriers to TB preventative care; and c) patient satisfaction. Qualitative data will be analysed using appropriate software where open coding will be applied to generate codes and themes. Thematic groupings will be developed and reviewed to identify emergent themes within each domain of the coding framework and quotes that best represent each domain. Thematic interpretation will include collaborative development of a coding framework and detailed coding of transcripts.

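### SAP 3.5 checks selection into the per-protocol set against the ITT set that contains it, and not explicitly by arm, so the check hides most of any selection

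*SAP*

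**What the plan says.** SAP 3.1 defines ITT as the strategy that "compares patients in the groups to which they were originally randomly assigned, irrespective of the treatment actually received". SAP 3.5 adds the handling of decliners: "Participants who decline to initiate 3HP after randomization will be counted as not accepting/completing treatment in the primary (ITT) analysis".

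For the per-protocol analysis, SAP 3.5, item 2, states that "participants who were randomized but declined to initiate treatment will be excluded from this analysis". It equates this analysis with the secondary outcome of treatment completion. Three outputs are planned: unadjusted risk ratios with 97.5% intervals, exact intervals against the 80% target, and risk ratios adjusted for baseline characteristics that are unbalanced or pre-specified. The item closes with the check at issue: "We will assess for differences in the ITT and PP analysis populations by comparing baseline characteristics such as age, sex", followed by ART status, time on ART and prior TB. It names no test or metric and no decliner group, and does not say whether the comparison is pooled or by arm.

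Two other balance assessments are described. SAP 3.3 covers all patients across arms. SAP 3.5, item 1, compares arms with Chi-square tests and ANOVA. Neither is stated to be among initiators.

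**The concern.** A selection check should show whether those who stay in the analysis differ from those who leave it. Here one group is a subset of the other, so most people appear on both sides and the contrast is diluted.

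The between-arm question matters more. Under the Day 1 procedures in the protocol, willingness to start 3HP is asked after the arm is known, so reasons for declining may depend on the arm. The per-protocol risk ratios are biased when initiators in one arm differ prognostically from initiators in another. A pooled comparison does not address that.

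At stake is the credibility of the treatment-completion comparison, a named secondary outcome, and the choice of covariates for its adjusted version. The protocol (Statistical Considerations, secondary analyses) defers details of inverse probability weighting for this estimand to the SAP. The SAP, which takes precedence, gives none. Covariate adjustment and this check are what remain.

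**Working it through.** The plan gives no figure for this check, so there is none to reproduce.

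**Inputs from the documents**
- Planned size: "a sample size of 552 participants per arm (N=1656 total) is required to provide power of 0.90 to detect this difference" (SAP 2.5).
- Decliners count as failures in the ITT analysis (SAP 3.5). The share declining, q, therefore cannot exceed 1 minus the accept-and-complete proportion.
- The lowest row of the SAP table titled "Power to detect 10% difference" has DOT 70% and choice 80%. Hence q is at most 30% in DOT and 20% in choice if those rates hold. SAT is not in the table.
- The second primary hypothesis, "The proportion of PLHIV who accept and complete 3HP can exceed 80% in a high HIV/TB burden setting", likewise puts q below 20% in an arm that achieves it.
- The value of q is not stated. The 5% (SAP) or 10% (protocol) loss in the sample-size text falls between consent and allocation, so it is not q.

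**Step 1: the identity.** With I the initiator mean and D the decliner mean of a baseline trait:

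ITT mean = (1 − q)·I + q·D, so per-protocol mean − ITT mean = I − [(1 − q)·I + q·D] = q·(I − D).

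The share of the gap hidden is 1 − q: 98% at q = 2%, 95% at 5%, 90% at 10%, 80% at 20% and 70% at 30%.

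**Step 2: an illustration (assumed).** Suppose a trait is present in 70% of initiators and 50% of decliners, with N = 1656. At q = 5% there are 83 decliners and 1573 initiators:
- ITT = (1573 × 0.70 + 83 × 0.50) / 1656 = 1142.6 / 1656 = 69.0%.
- Visible difference = 70.0 − 69.0 = 1.0 point, against a real gap of 20 points.

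The SAP names no test. If a pooled two-proportion test at two-sided 0.05 were used, treating the overlapping sets as independent, 20,000 simulated trials per row give:

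| q | Visible difference (points) | z, PP vs ITT | z, initiators vs decliners | Rejection rate, PP vs ITT | Rejection rate, initiators vs decliners |
|---|---|---|---|---|---|
| 2% | 0.4 | 0.25 | 2.47 | 0.00 | 0.68 |
| 5% | 1.0 | 0.62 | 3.84 | 0.00 | 0.96 |
| 10% | 2.0 | 1.21 | 5.24 | 0.001 | 0.999 |
| 20% | 4.0 | 2.32 | 6.87 | 0.85 | 1.00 |
| 30% | 6.0 | 3.32 | 7.77 | 0.999 | 1.00 |

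With no selection at all, the PP vs ITT test rejects 0.00 of the time at these shares, against about 0.05 for initiators vs decliners. Used that way, it is far too conservative.

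**Step 3: selection that differs by arm (assumed).** Take 552 per arm, a trait in 50% (276) of each arm, and 55 decliners per arm. Decliners carry the trait in 20% (DOT), 80% (SAT) and 50% (choice).
- DOT initiators: (276 − 11) / 497 = 265 / 497 = 53.3%.
- SAT initiators: (276 − 44) / 497 = 232 / 497 = 46.7%.
- Choice initiators: (276 − 27.5) / 497 = 50.0% (expected count).
- Pooled per-protocol: (265 + 232 + 248.5) / 1491 = 50.0%. Pooled ITT: 50.0%. Visible difference: zero.
- DOT vs SAT among initiators: 33 / 497 = 6.6 points, standard error √(0.25 × 2 / 497) = 3.17 points, z = 2.1.

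**The case against.** Five points can be made for the plan.

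1. **The diluted figure answers a real question: how far does excluding decliners shift the analysed population?** It also limits the bias from a measured trait. If the trait changes completion by 20 points (assumed), the 6.6-point imbalance in Step 3 moves the DOT–SAT completion difference by 6.6 × 0.20 = 1.3 points, against a minimum important difference of 10 points for choice vs DOT. This stands, and is a main reason to keep the severity modest.
2. **A reader might infer that the check conceals nearly all selection and will almost always report no difference.** The documents do not support that, because they give no decline share. At 20% declining, the 20-point gap is flagged in 85% of simulated trials.
3. **A reader might infer that an invalid test is planned, or that a null finding licenses the per-protocol result.** The sentence names no test, and no rule depends on its outcome. A descriptive table would satisfy it.
4. **Part of the remedy is already planned.** SAP 3.7 includes a "simple calculation of the proportion of patients randomized who accept treatment in each arm", and SAP 3.6 extends exploratory subgroups (sex, age, ART status, time on ART and prior TB among them) to secondary analyses. Acceptance by subgroup is the initiator–decliner contrast on the same five factors. The protocol's Reach analysis adds CD4 stratum and viral load suppression. This stands in part: those analyses are exploratory and not tied to judging the per-protocol arms.
5. **If q is reported, the gap can be recovered** as (per-protocol − ITT) / q. That is true of the pooled gap, but a pooled table cannot yield the differences between arms.

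The adjusted per-protocol risk ratios also help, but they depend on knowing which characteristics are unbalanced among initiators, and no described assessment is stated to look there.

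**Conclusion.** The point holds at modest severity. Under the operative definition in SAP 3.5, the stated comparison shows only the fraction q of any initiator–decliner difference. It hides 90% or more if at most 10% decline, and still 80% (choice) or 70% (DOT) at the upper limits implied by the planning rates. The dilution follows from the definitions alone; its size rests on a decline share that the documents do not give, and the limits hold only if the planning rates do. If the looser description of per-protocol in SAP 3.1 (strict adherence to the protocol) were applied, more people could be excluded and less would be hidden.

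The by-arm gap is the more important half: a pooled check can read zero while the arms being compared diverge.

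A reader might infer that the trial's main conclusion is at risk. It is not. ITT is the main approach, it counts decliners as failures, and no alpha level or sample size depends on this check.

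**What to change.** Replace the closing sentence of SAP 3.5, item 2, with two tables of the characteristics already listed there (age, sex, ART status, time on ART, prior TB):

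- (a) initiators against decliners, overall and within each arm, with counts and standardized differences;
- (b) initiators only, by arm.

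State that (b) is the basis for judging whether the per-protocol arms are comparable, and for identifying which characteristics count as unbalanced in the adjusted per-protocol risk ratios.

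The cost is one SAP sentence and one extra table from data already held. The downside is that the decliner columns will be imprecise if few decline, particularly by arm; reporting counts and standardized differences makes that visible.
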